Table 5:	Criteria for Clinically Notable Vital Sign Abnormalities for 12 to 15 Years Old	32
Table 6:	Criteria for Clinically Notable Vital Sign Abnormalities for 16 to 17 Years Old	32
Table 7:	Criteria for Clinically Notable Vital Sign Abnormalities for ≥ 18 Years Old.....	33
Table 8:	Statistical Analysis Plan Versions	34

LIST OF FIGURES

Figure 1:	Study Design Schema	11
-----------	---------------------------	----

LIST OF ABBREVIATIONS

Abbreviations	Definition
AE	adverse event
ANCOVA	analysis of covariance
ASR	application site reaction
BID	twice daily
BMI	Body Mass Index
BSA	body surface area
CDLQI	Children's Dermatology Life Quality Index
CI	confidence interval
CRF	case report form
CTCAE	Common Terminology Criteria for Adverse Events
DBP	diastolic blood pressure
DLQI	Dermatology Life Quality Index
eCRF	electronic case report form
FAS	Full Analysis Set
F-BSA	facial body surface area
F-PaGIC-V	facial assessment of Patient Global Impression of Change-Vitiligo
F-PhGVA	facial assessment of Physician Global Vitiligo Assessment
F-VASI	Face Vitiligo Area Scoring Index
F-VASI25/50/75/90	≥ 25%/50%/ 75%/ 90% improvement from baseline in Face Vitiligo Area Scoring Index score
HADS	Hospital Anxiety and Depression Scale
MedDRA	Medical Dictionary for Regulatory Activities
MI	multiple imputation
MMRM	mixed-effect model repeat measurement
NCI	National Cancer Institute
NRI	nonresponder imputation
Pa-GIC-V	Patient Global Impression of Change-Vitiligo
PD	pharmacodynamic
PhGVA	Physician Global Vitiligo Assessment
PK	pharmacokinetics
PP	per protocol

Abbreviations	Definition
PT	preferred term
SAP	Statistical Analysis Plan
SBP	systolic blood pressure
SOC	system organ class
T-BSA	total body surface area
TE	treatment-extension
TEAE	treatment-emergent adverse event
T-PaGIC-V	total body assessment of Patient Global Impression of Change-Vitiligo
T-PhGVA	total body assessment of Physician Global Vitiligo Assessment
TSQM	Treatment Satisfaction Questionnaire for Medication
T-VASI	total body Vitiligo Area Scoring Index
T-VASI25/50/75/90	≥ 25%/50%/ 75%/ 90% improvement in total body Vitiligo Area Scoring Index
VASI	Vitiligo Area Scoring Index
VitiQoL	Vitiligo-specific quality of life
VNS	Vitiligo Noticeability Scale
WHO-5	World Health Organization-Five Well-Being Index

1. INTRODUCTION

INCB 18424-306 is a randomized, vehicle-controlled study in adolescent and adult participants (age \geq 12 years) with nonsegmental vitiligo who have depigmented area including \geq 0.5% BSA on the face, \geq 0.5 F-VASI, \geq 3% BSA on nonfacial areas, \geq 3 T-VASI, and for whom total body involved vitiligo area (facial and nonfacial) does not exceed 10% BSA. Approximately 300 participants will be randomized 2:1 to receive initial study treatment (ruxolitinib cream 1.5% BID:vehicle; applied to depigmented vitiligo areas on the face and body up to 10% total BSA) for 24 weeks. Participants will be stratified by region (North America or Europe) and skin type (Fitzpatrick scale Type I and II vs Type III, IV, V, and VI). Adolescents (\geq 12 to $<$ 18 years) will make up at least 10% of the study population, and no more than 50% of participants will be $>$ 40 years old.

After completion of the Week 24 assessments, participants will be offered the opportunity to receive an additional 28 weeks of treatment extension with ruxolitinib cream 1.5% BID. To be eligible for the treatment extension, participants must have completed the baseline and Week 24 visit assessments, be compliant with study procedures, and not have any safety issues. The total treated area should not exceed 10% BSA (facial and nonfacial).

Participants who successfully complete the 52-week treatment in this study may be eligible to participate in a separate extension study to evaluate durability of effect and maintenance regimens.

The purpose of this SAP is to provide details of the statistical analyses that have been outlined in the study Protocol. The scope of this plan will be executed by the Department of Biostatistics or designee, and the analyses of PK will be executed by the Department of Clinical Pharmacokinetics or designee.

Another Phase 3 study, INCB 18424-307, has the identical study design as INCB 18424-306. This SAP applies to both INCB 18424-306 and INCB 18424-307 studies.

2. STUDY INFORMATION, OBJECTIVES, AND ENDPOINTS

2.1. Protocol and Case Report Form Version

This SAP is based on INCB 18424-306 and -307 Protocol Amendment 3-US-CA dated 13 MAR 2020, INCB 18424-306 CRF approved 04 JUN 2020, and INCB 18424-307 CRF approved 05 JUN 2020. Unless superseded by an amendment, this SAP will be effective for all subsequent Protocol amendments and CRF versions.

2.2. Objectives and Endpoints

Table 1 presents the objectives and endpoints.

Table 1: Objectives and Endpoints

Objectives	Endpoints
Primary	
To evaluate the efficacy of ruxolitinib cream in participants with vitiligo.	
 • Proportion of participants achieving F-VASI75 at Week 24.
Key Secondary	
To further assess the efficacy of ruxolitinib cream.	
 • Proportion of participants achieving F-VASI50 at Week 24. • Proportion of participants achieving F-VASI90 at Week 24. • Proportion of participants achieving T-VASI50 at Week 24. • Proportion of participants achieving a VNS of “4 – A lot less noticeable” or “5 – No longer noticeable” at Week 24. • Percentage change from baseline in F-BSA at Week 24.
Secondary	
To evaluate the safety and tolerability of ruxolitinib cream.	
 • The frequency and severity of AEs; physical examinations; vital signs; and laboratory data for hematology and serum chemistry.
To further assess the efficacy of ruxolitinib cream.	
 • Proportion of participants achieving F-VASI25/50/75/90 during the treatment period (double-blind and treatment extension periods). • Percentage change from baseline in F-VASI during the treatment period (double-blind and treatment extension periods). • Percentage change from baseline in F-BSA during the treatment period (double-blind and treatment extension periods). • Percentage change from baseline in T-VASI during the treatment period (double-blind and treatment extension periods). • Percentage change from baseline in T-BSA during the treatment period (double-blind and treatment extension periods). • Proportion of participants achieving T-VASI25/50/75/90 during the treatment period (double-blind and treatment extension periods). • Proportion of participants in each category of VNS during the treatment period (double-blind and treatment extension periods). • Change from baseline in DLQI (or CDLQI) during the treatment period (double-blind and treatment extension periods).
To evaluate the ruxolitinib PK in plasma after treatment of ruxolitinib cream.	
 • Population-based (trough) plasma concentrations of ruxolitinib at Weeks 4, 24, and 40.

Table 1: Objectives and Endpoints (Continued)

Objectives	Endpoints
Exploratory	
To further assess the efficacy of ruxolitinib cream.	
 • Proportion of participants achieving an F-PhGVA of clear (0) or almost clear (1) during the treatment period (double-blind and treatment extension periods). • Proportion of participants achieving a T-PhGVA of clear (0) or almost clear (1) during the treatment period (double-blind and treatment extension periods). • Proportion of participants in each F-PhGVA category during the treatment period (double-blind and treatment extension periods). • Proportion of participants in each T-PhGVA category during the treatment period (double-blind and treatment extension periods). • Proportion of participants who report F-PaGIC-V of very much improved or much improved during the treatment period (double-blind and treatment extension periods). • Proportion of participants in each F-PaGIC-V category during the treatment period (double-blind and treatment extension periods). • Proportion of participants who report T-PaGIC-V of very much improved or much improved during the treatment period (double-blind and treatment extension periods). • Proportion of participants in each T-PaGIC-V category during the treatment period (double-blind and treatment extension periods). • Proportion of participant in each category for the color-matching question during the treatment period (double-blind and treatment extension periods).
To determine the participants' quality of life.	
 • Change from baseline in WHO-5 during the treatment period (double-blind and treatment extension periods). • Actual measurements in TSQM during the treatment period (double-blind and treatment extension periods). • Change from baseline in VitiQoL during the treatment period (double-blind and treatment extension periods). • Change from baseline in HADS during the treatment period (double-blind and treatment extension periods).
To evaluate translational biomarkers in the blood of participants treated with ruxolitinib cream.	
 • Change from baseline in the expression of select biomarkers in peripheral blood at Weeks 12, 24, 40, and 52.

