3. OBJECTIVES AND ENDPOINTS

Table 8 presents the objectives and endpoints.

Table 8: Objectives and Endpoints

Objectives	Endpoints
Primary	
To evaluate the efficacy of ruxolitinib cream in participants with vitiligo.	
• Proportion of participants achieving F-VASI75 at Week 24.
Key Secondary	
To further assess the efficacy of ruxolitinib cream.	
• Proportion of participants achieving F-VASI50 at Week 24.• Proportion of participants achieving F-VASI90 at Week 24.• Proportion of participants achieving T-VASI50 at Week 24.• Proportion of participants achieving a VNS of “4 – A lot less noticeable” or “5 – No longer noticeable” at Week 24.• Percentage change from baseline in F-BSA at Week 24.
Secondary	
To evaluate the safety and tolerability of ruxolitinib cream.	
• The frequency, duration, and severity of AEs; physical examinations; vital signs; and laboratory data for hematology and serum chemistry.
To further assess the efficacy of ruxolitinib cream.	
• Proportion of participants achieving F-VASI25/50/75/90 during the treatment period (double-blind and treatment extension periods).• Percentage change from baseline in F-VASI during the treatment period (double-blind and treatment extension periods).• Percentage change from baseline in F-BSA during the treatment period (double-blind and treatment extension periods).• Percentage change from baseline in T-VASI during the treatment period (double-blind and treatment extension periods).• Percentage change from baseline in T-BSA during the treatment period (double-blind and treatment extension periods).• Proportion of participants achieving T-VASI25/50/75/90 during the treatment period (double-blind and treatment extension periods).• Proportion of participants in each category of VNS during the treatment period (double-blind and treatment extension periods).

Table 8: Objectives and Endpoints (Continued)

Objectives	Endpoints
Secondary (continued)	
To evaluate the ruxolitinib PK in plasma after treatment of ruxolitinib cream.	
Population-based (trough) plasma concentrations of ruxolitinib at Weeks 4, 24 and 40.
Exploratory	

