9.3. Recording and Follow-Up of Adverse Events and/or Serious Adverse Events

Adverse Event and Serious Adverse Event Recording

- An AE/SAE that begins or worsens after informed consent is signed should be recorded on the Adverse Event Form in the eCRF. Conditions that were present at the time informed consent was given should be recorded on the Medical History Form in the eCRF.
- When an AE/SAE occurs, it is the responsibility of the investigator to review all documentation (eg, hospital progress notes, laboratory reports, and diagnostics reports) related to the event.
- The investigator (or delegate) will then record all relevant AE/SAE information in the eCRF.
- It is **not** acceptable for the investigator to send photocopies of the participant's medical records to sponsor or designee in lieu of completing the AE eCRF page.
- There may be instances when copies of medical records for certain cases are requested. In this case, all participant identifiers, with the exception of the participant number, will be redacted on the copies of the medical records before submission.
- The investigator will attempt to establish a diagnosis of the event based on signs, symptoms, and/or other clinical information. Whenever possible, the diagnosis (not the individual signs/symptoms) will be documented as the AE/SAE. When a clear diagnosis cannot be identified, each sign or symptom should be reported as a separate AE/SAE.

To the extent possible, each AE/SAE should be evaluated to determine:

- The severity grade (CTCAE Grade 1 to 5). See below for further instructions on the assessment of intensity.
- Whether there is at least a reasonable possibility that the AE is related to the study drug: suspected (yes) or not suspected (no). See below for further instructions on the assessment of causality.
- The start and end dates, unless unresolved at final safety follow-up.
- The action taken with regard to study drug as a result of the AE/SAE(s).
- The event outcome (eg, not recovered/not resolved, recovered/resolved, recovering/resolving, recovered/resolved with sequelae, fatal, unknown).
- The seriousness, as per the SAE definition provided in Section 9.2.
- The action taken with regard to the event. Note: If an AE is treated with a concomitant medication or nondrug therapy, this action should be recorded on the Adverse Event Form, and the treatment should be specified on the appropriate eCRF (eg, Prior/Concomitant Medications, Procedures and Non-Drug Therapy).

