- The investigator is obligated to perform or arrange for the conduct of supplemental measurements and/or evaluations as medically indicated or as requested by the sponsor or designee to elucidate the nature and/or causality of the AE/SAE as fully as possible. This may include additional laboratory tests or investigations, histopathological examinations, or consultation with other healthcare professionals.
- If a participant dies during participation in the study or during a recognized safety follow-up period, the investigator will provide the sponsor or designee with a copy of any postmortem findings, including histopathology.
- New or updated information will be recorded in the originally completed eCRF.
- Any updated SAE data will be submitted to the sponsor or designee immediately, without undue delay, under no circumstances later than 24 hours following knowledge of the event.

- Once an AE is detected, it should be followed until it has resolved or until it is judged to be permanent; assessment should be made at each visit (or more frequently if necessary) of any changes in severity, the suspected relationship to the study drug, the interventions required to treat the event, and the outcome.
- When the severity of an AE changes over time for a reporting period (eg, between visits), each change in severity will be reported as a separate AE until the event resolves.

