8.2. Adverse Events

8.2.1. Adverse Event Definitions

A TEAE is any AE either reported for the first time or worsening of a pre-existing event after first application of study drug and within 30 days of the last dose of study drug. For participants who cross over treatments, the first application date is period-specific, and the end date is 30 days after the last application date in this period, or the first application date in the next period, whichever comes first. Analysis of AEs (as discussed below) will be limited to TEAEs,

but data listings will include all AEs regardless of their timing in relation to study drug application.

Adverse events will be tabulated by MedDRA PT and SOC. Severity of AEs will be graded using the NCI CTCAE. The CTCAE v5.0 is used for this study. The CTCAE reporting guidelines and grading details are available on the Cancer Therapy Evaluation Program website.

The subset of AEs considered by the investigator to be related to study drug will be considered to be treatment-related AEs. If the investigator does not specify the relationship of the AE to study drug, the AE will be considered to be treatment-related. The incidence of AEs and treatment-related AEs will be tabulated. Serious AEs will also be tabulated.

Any missing onset date, causality, or severity must be queried for resolution. Unresolved missing causality and severity will be handled according to the following rules:

- An unresolved missing causality will be considered treatment-related.
- An unresolved missing severity will be identified as an unknown severity.

For purposes of analysis, all AEs will be considered TEAEs unless the AE can unequivocally be defined as not treatment-emergent.

Application site reactions are AEs that occur at the site of drug application. A summary of ASRs will be provided. Exposure-adjusted summaries will be provided for the safety population including cumulative TEAEs.

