10.1. Changes to Protocol-Defined Analyses

- The FAS will be used to replace ITT in evaluation of the efficacy during DB period. The participants with only baseline but not any postbaseline assessments are excluded from the FAS. Those participants are not considered to be able to contribute to the efficacy analysis because of missing data in postbaseline visits.
- Multiple imputation will be used to replace the NRI to handle missing values in the analysis for primary and key secondary endpoints. Multiple imputation is able to provide unbiased estimates of the parameters under MAR.
- DLQI/CDLQI have been moved from exploratory endpoints to secondary endpoints.

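### AE duration is part of the protocol's secondary safety endpoint, but the SAP omits it undeclared and plans no summary of it by treatment group

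*SAP*

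**What the plan says.** The current protocol states the secondary safety endpoint twice in the same words, in Table 1 (Section 1) and Table 8 (Section 3): "The frequency, duration, and severity of AEs; physical examinations; vital signs; and laboratory data for hematology and serum chemistry".

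SAP 2.1 ties the analysis plan to that version: "This SAP is based on INCB 18424-306 and -307 Protocol Amendment 3-US-CA dated 13 MAR 2020". SAP 2.2, Table 1, then gives the endpoint as "The frequency and severity of AEs; physical examinations; vital signs; and laboratory data for hematology and serum chemistry".

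SAP 10.1 lists three departures from the protocol. Two concern the analysis population and the handling of missing data. The third is a change to the endpoint list: "DLQI/CDLQI have been moved from exploratory endpoints to secondary endpoints".

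For the analysis, SAP 8.2.1 says "The incidence of AEs and treatment-related AEs will be tabulated". For data collection, Protocol 9.3 asks that each event be evaluated, as far as possible, for "The start and end dates, unless unresolved at final safety follow-up". It adds that when severity varies over a reporting period, "each change in severity will be reported as a separate AE until the event resolves".

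**The concern.** The two endpoint statements are otherwise the same, and the SAP version lacks one component. The section of the SAP that exists to record departures does not mention it, although the DLQI entry shows that endpoint changes are recorded there. A component that the protocol names would therefore go unsummarised without explanation. The SAP states that it governs both INCB 18424-306 and INCB 18424-307, so this applies to both studies.

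What is at stake is the tolerability half of the objective. The cream is applied twice daily for up to 52 weeks, and the SAP gives application site reactions their own summaries. Two reactions of the same grade, relatedness and action taken, one brief and one persistent, would count identically in the planned tables.

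**Working it through.** The plan gives no figure to reproduce. The check sets the texts side by side and counts the planned outputs.

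**Where duration appears**

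| Place | AE duration |
|---|---|
| Protocol Table 1 and Table 8 | Part of the endpoint |
| Protocol 4.1 | Not named; type, frequency and severity are given, introduced as examples |
| Protocol 10.3.2 | No duration analysis; incidence by MedDRA term, with CTCAE grading |
| SAP 2.2, Table 1 | Absent |
| SAP 8.2.1 | No duration variable defined |
| SAP 10.1 | Change not listed (0 of 3 items) |

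**Planned summaries**

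- SAP 8.2.2 lists 8 items for the overall summary and 16 summaries by MedDRA term: 8 + 16 = 24 entries. None concerns how long an event lasted.
- Appendix A lists AE tables from 3.2.1.1.X to 3.2.11.1.X. Sixteen titles end in X and seven in Y: 16 + 7 = 23. None names duration.
- Every figure in Appendix A is an efficacy figure.
- The only duration that the SAP summarises is duration of treatment (SAP 6.4). Exposure-adjusted incidence divides by time at risk and does not describe event length.

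**Could the result be produced later?** Yes, because start and end dates are recorded. Three rules are missing, however:

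1. *Joining.* Under Protocol 9.3 one event whose severity changes becomes several records, so the length of a record is not always the length of an episode.
2. *End dates.* SAP 8.2.1 says "Any missing onset date, causality, or severity must be queried for resolution", which does not cover a missing end date.
3. *Ongoing events.* SAP 8.2.1 sets a period boundary for deciding which period an event belongs to, but does not say how to report an event still open when the double-blind period ends.

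**The case against.** The strongest reply is that the SAP removed no planned analysis, because the protocol never specified one. Protocol 10.3.2 plans only incidence, and Protocol 4.1 describes the safety endpoints without duration. The SAP agrees with both and departs only from the endpoint tables. This stands in part: the inconsistency begins in the protocol, and a reader who infers that the SAP deleted a specified analysis goes too far. But Protocol 10.3 calls itself a summary and leaves details to the SAP, and Section 4.1 gives examples. Neither removes duration from Tables 1 and 8, and the amendment log does not record its removal.

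Three other strong readings are tempting and are not supported:

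- *Duration will have no result at all.* Listings 2.7.1 (all adverse events) and 2.7.9 (application site reactions) are planned and may show dates. Their layout is in a separate document, so this is unknown. What can be said is that no summary by arm is planned.
- *A persistent reaction is invisible in the tables.* The tables also cover dose interruption, discontinuation, relatedness, seriousness and exposure-adjusted rates, so a troublesome long reaction could show there. Only reactions alike on all of these are indistinguishable.
- *Record splitting biases the results by a known factor.* One can invent a case: three 10-day records from one 30-day episode, 30 / 10 = 3. The pattern comes from no document, and nobody plans a record-level analysis. It shows why a joining rule is needed, and is not an error in the plan.

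It is also fair to say that there may be little to summarise. Protocol 2.4.2.2.3 reports no significant application site events in Phase 2, and SAP 8.1 allows a listing in place of a sparse table.

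**Conclusion.** The point holds as a mismatch between protocol and SAP with a small reporting gap. A protocol-stated component of the secondary safety endpoint is missing from the SAP endpoint, is not declared in SAP 10.1, and is in 0 of 23 AE tables. Participant listings may show it; no summary by treatment group will.

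The size is minor. The component is descriptive and has no bearing on alpha, power or the primary conclusion. It can be recovered without new data. The conclusion assumes that the table titles in Appendix A reflect their content, since the shells are not available. The documents do not show whether the omission was deliberate.

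**What to change.** Restore duration in SAP Table 1. Add to SAP 8.2.2 one descriptive table for the double-blind period, by treatment group, for application site reactions, and optionally for the TEAEs already tabulated at 1% or more. It should give episode duration and the number and percentage unresolved, under these rules:

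- Join consecutive records of the same preferred term that were split only because severity changed.
- Report events still open at the end of the period as ongoing, with the same cut-off in both arms. The SAP 8.2.1 boundary is worded for participants who cross over, so its use in the ruxolitinib arm should be stated.
- State how a missing end date is handled.

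Kaplan-Meier medians are optional. Align Protocol 4.1 with Tables 1 and 8.

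If the sponsor means to drop duration, the alternative is to declare this with a reason in SAP 10.1 and amend the protocol tables.

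The cost is programming time for one table. With about 300 participants randomised 2:1, the vehicle arm has about 300 / 3 = 100, so estimates will be imprecise if few reactions occur. Duration among participants who had an event is not a randomised comparison, and the table should be labelled descriptive.
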